21.0 Medical Devices	
21.1 *Does your study involve the use of any medical devices?	
○ Yes No	
22.0	

Alternative Treatments

€ Yes € No		
If Yes, describe.		
Acamprosate, naltrexone and disulfi	ram	
$^{2.2}$ *Is the study drug/device/pr	ocedure currently available without participating in	the study?
© Yes ◯ No		
If Yes, describe:		
Apremilast is currently marketed for	r treatment of moderate to severe plaque psoriasis.	
3.0 Data and Safety Monitoring	Į.	
23.1 *Describe the plan for monito	oring data and safety. (A plan is REQUIRED.)	
Data and Safety Monitoring		

Potential risks and benefits for participants

Stringent procedures will be followed to minimize the risk of adverse reactions for participants, including the following:

- Subjects will be excluded who are at increased risk through a thorough medical history, physical exam, including ECG, blood chemistry, complete blood count (CBC), liver function tests (LFT's), urinalysis, and urine toxicology screen for drug of abuse. Subjects with any conditions that would expose them to unusual risk (e.g., suicidal ideation, significant medical disorders, or pregnancy) will be excluded.
- Subjects will be carefully monitored by the P.I. and [name]., PharmD, Safety Monitor, during weekly laboratory meetings with all personnel involved in the study.
- A menstrual history, negative pregnancy test, and birth control will be documented in women to avoid giving study drugs to women with unrecognized pregnancies.
- Female subjects of childbearing potential will be instructed to use an effective (i.e double barrier) form of birth control for the duration of the study and for 2 weeks thereafter.
- Study medication will be administered according to a protocol reviewed for safety by the FDA and conducted under an IND. The medication studied is considered safe when used in accordance with the procedures to be employed in the study.
- Subjects will be advised neither to drive a car nor operate complex machinery until they have gained sufficient experience on drug to gauge whether or not it affects their mental and/or motor performance adversely.
- The clinical ratings and blood tests will be performed by experienced personnel to minimize complications and unnecessary fatigue and distress.
- At the follow-up visit, subjects who report significantly increased alcohol consumption or serious psychiatric/medical symptoms will be offered a referral to treatment specific to their needs.

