Importantly, the research group has a well-established record of patient safety in the conduct of similar human laboratory studies and pharmacological trials. Apremilast is considered safe when used in accordance with the procedures to be employed in the study and exposure to drug is of brief duration i.e., 10 days. Subjects with any conditions which would represent increased risk, e. g. significant medical or psychiatric disorders, pregnancy, or suicidal ideation, will not be admitted to the study. The most common reactions are typically more unpleasant than dangerous. Stringent procedures will be followed to minimize the risk of adverse reactions. These include the following: 1.) a medical history; 2.) a physical exam, including EKG, blood chemistry, complete blood count (CBC), liver function tests (LFT's), urinalysis, and urine toxicology screen for drug of abuse; 3.) a menstrual history, negative pregnancy test prior to study admission, and birth control will be documented in women of childbearing potential, to avoid giving fenofibrate to women with unrecognized pregnancies; 4.)Women of child bearing potential will advised to use an effective method of birth control for study duration and for 2 weeks thereafter; 5.) close medical supervision, and if significant adverse drug events occur the study physician will evaluate the subject's condition and may discontinue the medication. Any clinically significant abnormalities persisting at the end of the study will be followed by the investigator until resolution or until a clinically stable endpoint is reached. The clinical ratings and blood tests will

be performed by experienced personnel to minimize complications and unnecessary fatigue and distress.

All subjects are required to be abstinent a minimum of 3 days prior to the lab session. Depending upon the extent of alcohol use and individual tolerance some subjects may be at risk for alcohol withdrawal. To protect against these risks each subject will be carefully evaluated with the CIWA by an experienced study physician at the screening and lab study visits for potential withdrawal risk and symptoms, including vital signs, time of last drink, quantity consumed, pattern of drinking, and history of alcohol withdrawal. In the unlikely event that significant (CIWA > 8) withdrawal symptoms are present, subjects will not proceed with the study and will be referred to a nearby detox facility.

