37.10 Inclusion Criteria

*Use the link below to add inclusion criteria.

Order Number	Criteria
1	 Male or female volunteers, 18-65 years of age. Meets DSM-5 criteria for current alcohol use disorder of moderate or greater severity (AUD-MS). In the month prior to screening, reports drinking ≥ 21 standard drinks per week if male, ≥ 14 if female, with at least one heavy drinking day (≥ 5 males, ≥ 4 females) per week. Subjects will not be seeking treatment because the medication studies are not treatment trials, and to avoid exposing treatment-seekers to alcohol cues Subjects must be abstinent a minimum of 3 days (but not more than 7 days) prior to the human lab session. Negative BAC and a CIWA score of < 8 at time of lab session to eliminate acute alcohol or withdrawal effects on dependent measures. In acceptable health in the judgment of the study physician, on the basis of interview, medical history, physical exam, EKG, routine urine and blood chemistry. Females with childbearing potential must have a negative pregnancy test on the screening, randomization, and lab session visits and agree to use effective birth control for the duration required by a given study. Able to provide informed consent and understand questionnaires and study procedures in English. Willing to comply with the provisions of the protocol and take daily oral medication.

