- Sexually active female subjects with childbearing potential who are pregnant, nursing, or refuse to use effective methods of birth control for the duration required by a specific protocol.
- No fixed domicile and/or no availability by home or mobile telephone.
- History of hypersensitivity to the study drug or the ingredients.
- · Failure to take double-blind medication as prescribed.

Exclusion Criteria:

- Active suicidal ideation, as systematically assessed with the Columbia Suicide Severity Rating Scale.
- Meets DSM-5 criteria for a major psychiatric disorder, including mood or anxiety disorders or substance use disorders other than alcohol or nicotine.
- Has a urine drug screen (UDS) positive for substances of abuse other than alcohol.
- Significant medical disorders that will increase potential risk or interfere with study participation as determined by the study physician.
- · History of seizure disorders.
- Liver function tests more than 3 times the upper limit of normal or elevated bilirubin.
- Treatment within the month prior to screening with (1) an investigational drug, (2) medications which may negatively interact with study medications, or (3) drugs that may influence study outcomes (e.g., disulfiram [Antabuse], naltrexone [ReVia], acamprosate [Campral], anticonvulsants, or antidepressants).
- Ongoing treatment with medications that may increase risk, including prescribed, over-the-counter, and herbal preparations, as determined by the study physician.
- Sexually active female subjects with childbearing potential who are pregnant, nursing, or refuse to use effective methods of birth control for the duration required by a specific protocol.
- No fixed domicile and/or no availability by home or mobile telephone.
- History of hypersensitivity to the study drug or the ingredients.
- Failure to take double-blind medication as prescribed.

9.1 *Will ANY specimens, other than blood, be obtained for this study? © Yes © No	Ographic.		

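### The only rule that excludes nursing women is limited to sexually active women of childbearing potential, so some nursing women meet no written exclusion

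*Protocol*

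**What the plan says.** The exclusion list that follows Protocol section 37.10 contains one bullet on pregnancy, nursing and contraception. It is printed twice with the same wording and excludes "Sexually active female subjects with childbearing potential who are pregnant, nursing, or refuse to use effective methods of birth control" for the period that the protocol requires.

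The related statements elsewhere in the Protocol are these:

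- **Section 37.10, inclusion criteria.** "Females with childbearing potential must have a negative pregnancy test on the screening, randomization, and lab session visits", and they must also "agree to use effective birth control for the duration required by a given study". Sexual activity is not a condition, and nursing is not mentioned.
- **Section 23.1, data and safety monitoring.** "Subjects with any conditions that would expose them to unusual risk (e.g., suicidal ideation, significant medical disorders, or pregnancy) will be excluded". On contraception: "Female subjects of childbearing potential will be instructed to use an effective (i.e double barrier) form of birth control". Neither sentence depends on sexual activity, and neither mentions nursing.
- **Section 34.5, minimizing risks.** "Subjects with any conditions which would represent increased risk, e. g. significant medical or psychiatric disorders, pregnancy, or suicidal ideation, will not be admitted". On contraception: "Women of child bearing potential will advised to use an effective method of birth control for study duration and for 2 weeks thereafter". Again there is no sexual-activity condition and no mention of nursing.

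The only entry on contraception in the IRB Summary of Amendments changes its duration. No listed entry concerns nursing or the qualifier in the exclusion bullet. The SAP is silent on eligibility.

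**The concern.** Grammatically, the opening words of the bullet define who is covered, and the three conditions then apply only within that group. Sexual activity and childbearing potential bear on whether contraception is needed. They have no bearing on whether a woman is nursing. A qualifier suited to one condition has been attached to all three.

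By naming nursing women, the sponsor shows that it meant to keep them out. If the bullet is followed exactly, part of that group is let through, and a nursing woman could be randomised and sent home with a blistercard of study drug. What is at stake is participant protection and a clear eligibility rule for the staff who apply it.

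**Working it through.** No figure is involved, so the check is one of logic. A subject is eligible only if she meets every inclusion criterion and no exclusion criterion. Each case below assumes that all other criteria are met.

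| Case | Inclusion item (37.10) | Exclusion bullet (37) | Other text | Result as written |
|---|---|---|---|---|
| A. Nursing, childbearing potential, not sexually active, tests negative, agrees to contraception | Met | Not triggered | None names nursing | Eligible |
| B. As A, but sexually active | Met | Triggered | – | Excluded |
| C. Nursing, judged not of childbearing potential (for example sterilised), sexually active or not | Does not apply | Not triggered | None names nursing | Eligible |
| D. Pregnant, not sexually active | Fails the pregnancy test | Not triggered | 23.1 and 34.5 bar pregnancy | Not eligible |
| E. Not nursing, childbearing potential, not sexually active, declines contraception | Fails | Not triggered | 23.1 and 34.5 give instructions or advice to all such women | Not eligible |

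**Nursing (A, B, C).** A and B differ only in sexual activity, which has nothing to do with nursing, yet one is eligible and the other is not. C shows that the childbearing-potential part of the qualifier opens the same gap. A search of both documents finds lactation only in this bullet. The other uses of the word belong to a form section about nursing and allied health research.

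**Pregnancy (D).** The qualifier has no practical effect here. The inclusion tests at three visits and the statements in 23.1 and 34.5 close the gap.

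**Contraception (E).** The exclusion bullet covers sexually active women only, whereas 37.10, 23.1 and 34.5 cover all women of childbearing potential. The scopes differ, but the rules can be applied together, and the broader inclusion rule decides the case.

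The nursing condition is thus the only one of the three with no backup elsewhere in the text, and so the only one for which the qualifier changes who is eligible.

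**The case against.** The strongest reply is that a study physician would stop such a woman. Section 37.10 makes entry depend on the physician's view of her health after interview, history and examination. The exclusion list leaves significant medical disorders to the physician. The risk clauses in 23.1 and 34.5 give examples rather than a closed list, and a menstrual history is documented. Nursing could well come to light at any of these points. The consent form was not among the pages available for this review and may also address it.

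This stands in part. It would be too strong to infer that the protocol has no means of detecting or acting on nursing. But nursing is neither ill health nor a disorder, none of these clauses names it, and discretion permits a refusal without requiring one. A consent form would not in any case replace a written eligibility criterion.

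A reader might also infer that the two lists give opposite decisions for a woman who is not sexually active and declines contraception, so that her entry depends on which list staff use. The documents do not support that. Not triggering an exclusion does not make her eligible: she fails section 37.10 and cannot enter.

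Nor is there a link to stratification by sex, which the amendment summary adds. Whether a rare nursing woman may enter does not affect stratified randomisation or the craving analysis.

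Finally, the number affected must be very small. The woman would have to be nursing, outside the qualifier, drinking at least 14 standard drinks a week, and cleared by the physician. This stands, and it limits the weight of the point.

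**Conclusion.** The point holds for nursing. Followed exactly, the exclusion bullet does not give the protection that it names: a nursing woman who is not sexually active, or not of childbearing potential, meets no written exclusion. For pregnancy the fault is one of wording without consequence. For contraception it is an inconsistency of scope that does not change who is eligible.

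Few if any of the 50 subjects are likely to be affected. The documents give no rate from which to calculate an expected number, so this is a judgement from the combination of conditions required. There is no effect on the sample size or on the statistical analysis.

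The conclusion assumes that the bullet is read literally, that both lists must be satisfied, and that no eligibility text outside the reviewed documents covers nursing.

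**What to change.** Reword the one bullet in the exclusion list of section 37, in both places where it is printed:

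1. State the pregnancy and nursing conditions on their own, outside the qualifier on sexual activity and childbearing potential.
2. Make contraception a separate condition and reconcile its scope with sections 37.10, 23.1 and 34.5. Those three already share one scope, so only this bullet is out of line. The investigators should decide the scope and the method of contraception.

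The cost is an edit to one criterion and, at most, the loss of a very few otherwise eligible women. No procedure, sample size or analysis changes.

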### Descriptors (Type, Condition, Amount) - if Yes, may meet criteria for Exempt, Category 4 Genetic Analysis Genomic Analysis Proteomic Analysis Cells Proteimen Type (Check all that apply) Category Proteimen Type (Check all that apply)			
*With regard to human specimens, check all that apply. Identifiable (patient identifiers (Name, Medical Record Number), Family History (Pedigree), Treatment and Outcome Data) Unidentifable (Demographics (Race, Gender, Age), Diagnosis, Histopathology, Specimen Descriptors (Type, Condition, Amount) - if Yes, may meet criteria for Exempt, Category 4 Genetic Analysis Genomic Analysis Proteomic Analysis Proteomic Analysis C2 *Specimen Type (Check all that apply)	⊙ Y	∕es Ω No	
*With regard to human specimens, check all that apply. Identifiable (patient identifiers (Name, Medical Record Number), Family History (Pedigree), Treatment and Outcome Data) Unidentifiable (Demographics (Race, Gender, Age), Diagnosis, Histopathology, Specimen Descriptors (Type, Condition, Amount) - if Yes, may meet criteria for Exempt, Category 4 Genetic Analysis Genomic Analysis Proteomic Analysis 2.2 *Specimen Type (Check all that apply)	0.0	Human Specimens and Cell Lines Detail	
☐ Identifiable (patient identifiers (Name, Medical Record Number), Family History (Pedigree), Treatment and Outcome Data) ☑ Unidentifable (Demographics (Race, Gender, Age), Diagnosis, Histopathology, Specimen Descriptors (Type, Condition, Amount) - if Yes, may meet criteria for Exempt, Category 4 ☐ Genetic Analysis ☐ Genomic Analysis ☐ Proteomic Analysis ☐ Proteomic Analysis ☐ Cells ☐ Cells	0.1	Human Specimens	
Treatment and Outcome Data) Unidentifable (Demographics (Race, Gender, Age), Diagnosis, Histopathology, Specimen Descriptors (Type, Condition, Amount) - if Yes, may meet criteria for Exempt, Category 4 Genetic Analysis Genomic Analysis Proteomic Analysis Proteomic Analysis Cells	*Wit	th regard to human specimens, check all that apply.	
Descriptors (Type, Condition, Amount) - if Yes, may meet criteria for Exempt, Category 4 Genetic Analysis Genomic Analysis Proteomic Analysis 2.2 *Specimen Type (Check all that apply) Cells	,,,,		
Genomic Analysis Proteomic Analysis 2.2 *Specimen Type (Check all that apply) Cells	C	Descriptors (Type, Condition, Amount) - if Yes, may meet criteria for Exempt, Category 4	
Proteomic Analysis 0.2 *Specimen Type (Check all that apply) Cells			
□ Cells			
	0.2	*Specimen Type (Check all that apply)	

Hair / Nails	
☑ Saliva	
[Semen	
✓ Urine	
☐ Tissue	
Fluid	
Bone Marrow Aspirate	
Other	
If fluid, tissue or other, describe.	
40.3 *Will the specimens come from samples originally obtained for clinical purposes?	
○ Yes ② No	
40.4 If Yes, describe how the samples were obtained and if informed consent was required.	
40.5 If No, where will the specimens come from?	
The samples will be obtained for research purposes only during a subject's study visit at the lab. Subjects will provide saliva samples, urine samples, and will undergo blood draws all of which will be obtained at the lab. Informed consent will be required before any of the above-listed procedures are undertaken.	
40.6 *Will specimens be maintained in such a way that the subjects can be identified?	
♥ Yes ♥ No	
If Yes, how will confidentiality be preserved?	
Subjects initials, study number and age are used as sample identifiers. No name-identifying information will be used in sample collection, documentation, analysis or storage.	
40.7 *Will specimens be transferred to or from a Scripps Health facility? (If Yes, please complete a Mate Transfer Agreement.)	rials
○ Yes ⊙ No	
If Yes, how will specimens be identified?	
If Yes, to which institution will specimens be transferred?	
TSRI	
Other:	
40.8 *Will this study involve human stem cells? (If 'Yes', attach a copy of the ESCRO approval to the Ini Review Submission Form)	tial
○ Yes ⑤ No	
If Yes, are the human stem cells derived from human embryonic tissue?	
ar res, are the number stem cons utilited from number class forme ussue.	

C Yes C No
If not from embryonic tissue, are the cells pluripotent or capable of being de-differentiated into pluripotent cells?
O Yes O No
40.9 *Does this study involve established human cell lines?
O Yes O No
If Yes, name the cell lines:
If Yes, will human cell lines be obtained from a public repository or a public source? O Yes O No
Will these cell lines or data be linked directly to the subject from whom they were obtained?
O Yes O No
*Will saved samples or their derivatives have the potential to produce profits for the investigators or Scripps?
O Yes O No
40.11 *Does this study involve the storage of genetic data in electronic form?
O Yes O No
*Does this study involve gene transfer or recombinant DNA use in INDIVIDUAL SUBJECTS in a CLINICAL TRIAL?
O Yes • No
If Yes, then review by an Institutional Biosafety Committee will also be required. To view information on Institutional Biosafety Review of Protocols Involving Gene Transfer Or Recombinant DNA (Appendix M of the NIH Guidelines), click on the Help bubble to the right.
40.13 If Yes, explain.
*Does the research protocol involve the use of RECOMBINANT DNA TECHNOLOGY or BIOLOGICAL AGENTS or materials that may be infectious in the clinical setting?
○ Yes ② No
List infectious agent or rDNA vector.

41.0 Funding Source (If you are a Principal Investigator receiving a Federal funded grant for collaborative sites to conduct Human Subjects Research, contact the IRB office. You will need to submit IRB documents from the collaborating institution.)

federal government, National Institutes of Health, National Science Foundation, US military - such as Department of Defense, etc.), the source(s) MUST be entered in this section. 41.1 *Is this study funded by a commercial sponsor? O Yes O No 41.2 *Is this study funded by a grant? Yes □ No *Is this an SCMG grant? O Yes 💿 No If this study is funded by a grant, are you the PI receiving the grant? 1 Yes O No If you are the PI receiving the grant, will any other projects in the grant use human subjects? Yes ○ No *If you are the PI for the entire grant, and checked 'Yes' to 'Human Subjects', please submit a copy of the entire grant. 41.3 *Status of funding: Please select one. Applied/Pending Approved O Not Applicable 41.4 Sponsor Protocol Number: 41.5 Grant Number: GRANT12116859 41.6 *Granting Agency/Sponsor (You can select more than one agency.) (If your agency is not in the list, click on the help bubble to the right.) If Departmental Funds are being used, click on 'Private' and choose 'Departmental Funds'. *Note: All studies must have an identifiable source of funding or they cannot be reviewed. Fill in the matrix below. Pass Sponsor Protocol Data Funding Monitoring **Auditing Through** Control Coordination Funding Commercial

IMPORTANT: If ANY funding for this project is coming from a Federal source (federal agency,

Federal or State	National Institute on Alcohol Abuse and Alcoholism		a	ō	(,ca	TO.	D.	
Private								
CRO								
Department funds								
41.7 Proposed Funding Date - BEGIN								
02/01/2017								
41.8 Proposed Funding Date - END								
01/31/2022								
41.9 Are part of or all activities in this proposal funded by a training grant?								
O Yes 6 No								

NCT03175549

Medication Development in Alcoholism: Apremilast versus Placebo

IRB Summary of Amendments-06/01/2017-05/08/2020

Summary of Amendments for NCT03175549

2017 Continuing Review Application-Prior to Study Initiation

Submitted on 06/01/2017/Approved on 06/19/2017

In the current application, we propose amending the final fixed dose of apremilast from 60 mg (30 mg/bid) for 5 days to a final fixed dose of 100 mg (50 mg/bid) for 5 days based on the pre-clinical data.

Animal data showed apremilast in dose of 10 mg/kg (human equivalent of 56 mg per day) was ineffective for reducing alcohol consumption and achieved efficacy in dose of 20 mg/kg which equivalents to human dose of 112 mg per day. This information was communicated to [name] in a personal email correspondence dated 05/26/17 from [name], an INIA collaborator at the University of Texas-Austin.

We searched the Clinical Pharmacology and Biopharmaceutical Review for apremilast and noted doses up to 100 mg per day have been studied. A series of studies showed any side effects (primarily diarrhea) are successfully reduced through dose titration and dosing on a twice a day schedule. Therefore, we are requesting IRB approval to treat 25 subjects on 5 days of a final fixed dose of 100 mg (50 mg BID) per day after a 7-day titration starting at 10 mg per day and increasing in 10 mg doses and 25 subjects on placebo. The titration to 100 mg per day will be according to the following schedule:

Day 1: 10 mg in morning

Day 2: 10 mg in morning and 10 mg in evening

Day 3: 10 mg in morning and 20 mg in evening

Day 4: 20 mg in morning and 20 mg in evening

Day 5: 20 mg in morning and 30 mg in evening

Day 6: 30 mg in morning and 30 mg in evening

Day 7: 30 mg in morning and 40 mg in evening

Day 8: 40 mg in morning and 40 mg in evening

Day 9: 40 mg in morning and 50 mg in evening

Day 10: 50 mg in morning and 50 mg in evening

Day 11: 50 mg in morning and 50 mg in evening

Day 12: 50 mg in morning and 50 mg in evening

Day 13: 50 mg in morning and 50 mg in evening

Day 14: 50 mg in morning and 50 mg in evening

Based on this titration schedule, we request modifying the duration of study drug administration from 10 days to 14 days.

Amendment-Prior to Study Initiation

Submitted on 07/20201/Approved on 08/11/2017

- -Added [name] as the Sub Investigator and Study Contact Person.
- -Changed the visit schedule.
- -Removed the Structured Clinical Interview for the DSM-IV (SCID) and replaced it with the Mini International Neuropsychiatric Interview (MINI) for DSM-V criteria.
- -Added the Columbia Suicide Severity Rating Scale (CSSRS) to the screening visit.
- -Removed the Profile of Mood States (POMS) from the self-report battery.
- -Added that subjects will be stratified by sex and by High-sensitivity C-reactive Protein (hs-CRP).
- -Added obtaining blood to visits two and four.
- -Added Cytokine analysis that will be performed at the end of the study by [name] at Temple University's School of Medicine.
- -Added medication over-encapsulation by Austin Compounding Pharmacy in Austin, TX.
- -Eliminated the need for women of child bearing age to use an effective form of birth control for 2 weeks following study duration. Revised to through study duration.
- -Removed "History of Seizure Disorder" from exclusion criteria.
- -Changed recruitment website from www.pearsoncenter.org to www.tsriaddiction.com.

- -Clinicaltrials.gov number obtained NCT03175549
- -Added a urine drug screen (UDS) at visit two.
- -Added the Columbia Suicide Severity Rating Scale (CSSRS) at visit four

Amendment-Prior to Study Initiation

Submitted on 09/28/2017/Approved on 10/13/2017

-Changed the dose range from 10 mg to 100mg/day to 10 mg to 90 mg/day and revised the dosing schedule.

Amendment

Submitted on 05/17/2018/Approved on 06/08/2018

Revised upper age limit to include subjects above the age of 65.

Revised the exclusionary criteria regarding positive urine drug screens to allow subjects who test positive for THC to participate in the study as long as they do not meet DSM-V criteria for cannabis use disorder at a moderate level or greater, and that these subjects agree to maintain three days of abstinence from cannabis prior to the laboratory session at the fourth visit of the study.

Amendment

Submitted on 08/30/2018/Approved on 10/12/2018

Obtained permission to collect serum at Visit 2 and Visit 4 to assay endotoxins to rule out a factor other than alcohol as a source of abnormal cytokine activity.

Amendment

Submitted on 05/15/2019/Approved on 07/12/2019

Expanded the inclusion criteria to enroll subjects who do not meet current criteria for depression who have been on a stable dose of anti-depressant medication for at least 3 months.

Amendment

Submitted on 04/15/2020/Approved on 05/08/2020

Modified exclusionary criteria to exclude subjects with a total score of less than or equal to 30 on the Alcohol Craving Questionnaire (ACQ) at their screening visit (Visit 1).

We had 16 other IRB amendments/approvals for recruitment advertisements and administrative issues such as staff changes.
